8.5 Physical Examination Findings

Physical examination include a general review of the following body systems (at minimum): head and neck, cardiovascular, respiratory, gastrointestinal, brief neurological and general appearance, unless a symptom-oriented physical exam is indicated.

Physical examination findings will be presented in a listing by cohort, subject and visit and clinically significant physical examinations will be presented in a separate listing.

9 PSYCHIATRIC ASSESSMENTS AND ANALYSIS

Unless otherwise specified, all available psychiatric assessments and analysis will be presented for the Safety population. Listings will be based on the Randomized population.

Missing data for subjects who are administered all scheduled study treatments will be considered as random non-informative missing for analysis purposes. Missing values will be examined on a case-by-case basis to confirm this. Reasons for missing data will be displayed in the listings. No further imputation will be applied to any missing values.

Assessments done outside the acceptable visit windows may be excluded from by-time point summary statistics; this will be determined on a case-by-case basis prior to unblinding.

Analyses will be based on actual assessment times, except for predose (baseline) times, which will automatically be considered as time 0 as appropriate for analysis. If the actual time is missing, the nominal time will be used.

9.1 Brief Psychiatric Rating Scale (BPRS)

9.1.1 BPRS Assessment

The BPRS scale is designed for the assessment of psychiatric symptoms or disorders (e.g., depression, anxiety, hallucinations, and unusual behavior).

The BPRS should be completed at Screening, Check-in on Day -2, 7 and 14. It will also be completed at approximately 6 and 24 h after dosing on Days 1, 7, and 14.

Baseline will be considered to be on Day -1.

Table 5: BPRS Details

Scale	Number of Items	Score Range Per Item	Total Possible Score	Scoring Interpretation	Data Collection
Brief Psychiatric Rating Scale (BPRS)	18 Items	1-7 point Likert scale 1=not present 2=very mild 3=mild 4=moderate 5=moderately severe 6=severe 7=extremely severe	126	Severity increases with increasing score A score of 18 is generally expected for healthy volunteers. Scores ≥ 25 reflect the presence of psychiatric symptoms and should be considered exclusionary Total Score cutoff criteria for patients diagnosed with schizophrenia or experiencing psychosis are: Mildly ill ≥ 31 Moderately ill ≥ 41 Markedly ill ≥ 53 In- or out patients with paranoid, disorganized or undifferentiated schizophrenia (DSM-IV), BPRS total score ≥ 36 , BPRS psychotic subscore ≥ 23 and at least two BPRS psychosis items $\geq 4^1$	Score for each item (1-7) Score Range: 18-126 Cutoff Score: ≥ 25 If an item is not assessed, the BPRS Total Score will not be computed

9.1.2 BPRS Visit Windows

The acceptable windows for BPRS will be within 2 h following the 6 hours nominal time point and within 3 h prior to next dose for the 24 h time point. All the 24 h postdose assessments are intended to be completed prior to next day dosing as applicable.

Psychiatric assessments should be carried out in the following order when required: (1) 3MS, (2) CADSS, (3) BPRS, (4) C-SSRS.

9.1.3 BPRS Endpoints

Derived endpoints will include:

- BPRS_TS_{CFB} = Total Score Change from Baseline (CFB) = BPRS_TS at each postdose time point – BPRS_TS_B at baseline
- BPRS_TS%_{CFB} = Total Score Percent Change from Baseline (CFB)

9.1.4 BPRS Analysis

Tables and listings will be presented for absolute values and derived endpoints described below. Inferential analysis will be provided for the derived endpoints (refer to SAP Section 9.6 for more detailed information).

In addition, a table and listing with Number of Subjects excluded at Screening (i.e., Number of subjects with BPRS_TS at Screening ≥ 25) will be presented.

9.2 Clinician Administered Dissociative States Scale (CADSS)

9.2.1 CADSS Assessment

The CADSS scale is designed for the assessment of dissociative states in adults.

The CADSS will be completed at Screening, Check-in on Day -2, and at approximately 6 and 24 h after dosing on Day 1. The CADSS will also be completed prior to dosing and at approximately 6 and 24 h after dosing on Days 7 and 14.

Baseline will be considered to be on Day -1.

Table 5: CADSS Details

Scale	Number of Items	Score Range Per Item	Total Possible Score	Scoring Interpretation	Data Collection
Clinician Administered Dissociative States Scale (CADSS)	23	0-4 point Likert scale 0=not at all 1=mild 2=moderate 3=severe 4=extreme	92	Severity increases with increasing score No official cut off criteria for scoring Baseline scores for normal healthy males were 1.67 (2.96) ²	
 • Score for each item (0-4) Score Range: 0-92 (general dissociation) ○ Of note Items can be segregated into factors e.g. Altered visual and auditory perception (items 2, 9, 10, 11, 16, 18) ○ Altered time and perception (Items 1, 12, 15) Depersonalization (Items 3, 4, 5, 6, 20)³

9.2.2 CADSS Visit Windows

The acceptable window for CADSS will be within 2 hours following the 6 h nominal timepoint and within 3 h prior to next dose for the 24 h time point. All of the 24 h postdose assessments are intended to be completed prior to next day dosing as applicable.

Psychiatric assessments should be carried out in the following order when required: (1) 3MS, (2) CADSS, (3) BPRS, (4) C-SSRS.

9.2.3 CADSS Endpoints

Derived endpoints will include:

- CADSS_TS_{CFB} = Total Score Change from Baseline (CFB) = CADSS_TS at each postdose time point – CADSS_TS_B at baseline
- CADSS_TS%_{CFB} = Total Score Percent Change from Baseline (CFB)

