3.5 Determination of Sample Size

No formal sample size analysis was performed. It is estimated that approximately 24 subjects should be sufficient to meet the objectives of the study.

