5.3 Baseline

Unless otherwise specified, the baseline value will be defined as the last non-missing evaluation prior to the first dose of study drug, including unscheduled assessment(s), if applicable.

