9.2.4 CADSS Analysis

Tables and listings will be presented for absolute values and derived endpoints described below. Inferential analysis will be provided for the derived endpoints (refer to SAP Section 9.6 for more detailed information).

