9.6 Psychiatric Assessments Analysis

Psychiatric measures at each time point will be summarized by treatment (placebo and each dose of TMP-301) using descriptive statistics and presented graphically. Derived endpoints will also be summarized by treatment using descriptive statistics. Only summary statistics will be output for E_{max} TE_{max} , E_{min} and TE_{min} . Descriptive statistics will include n, mean, standard error (SE), minimum, first quartile (Q1), median, third quartile (Q3) and maximum for all psychiatric assessment values, and endpoints other than TE_{max} and TE_{min} . For TE_{max} and TE_{min} , minimum, Q1, median, Q3 and maximum will be output.

A mixed-effects model for a parallel study design will be used to compare the derived endpoints between treatments (e.g., BPRS_TS_{CFB}, BPRS_TS%_{CFB}, CADSS_TS_{CFB}, CADSS_TS%_{CFB}, 3MS_TS_{CFB}, and 3MS_TS%_{CFB}). The model will include treatment (dosing group), day, and dose (1st or 2nd) as fixed effects, and the baseline measurement as a covariate. P-values for key components of variance, least-square means (LSMeans), and 95% CI for contrasts will be output. For each endpoint, the following comparisons will be made:

- Contrast 1: TMP-301 50 mg BID vs. Pooled Placebo
- Contrast 2: TMP-301 50 mg QD vs. TMP-301 50 mg BID
- Contrast 3: TMP-301 50 mg QD vs. Pooled Placebo
- Contrast 4: TMP-301 XX mg vs. TMP-301 50 mg BID
- Contrast 5: TMP-301 XX mg vs. TMP-301 50 mg QD
- Contrast 6: TMP-301 XX mg vs. Pooled Placebo

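### CADSS percent change is modelled with no rule for a zero baseline; the Day -1 baseline statements and the SAP's 3MS change formula and item scoring also need correcting

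*SAP*

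**What the plan says.** **CADSS.** SAP 9.2.1 describes 23 items scored 0 to 4, total 0 to 92, and adds "Baseline scores for normal healthy males were 1.67 (2.96". The bracketed figure is not labelled. SAP 9.2.3 lists absolute change and percent change as derived endpoints, the latter as "CADSS_TS%_{CFB} = Total Score Percent Change from Baseline (CFB". SAP 9.2.4 states "Inferential analysis will be provided for the derived endpoints". SAP 9.6 states "A mixed-effects model for a parallel study design will be used to compare the derived endpoints between treatments" and names CADSS percent change among them, with baseline as a covariate and 95% confidence intervals for the contrasts. For subjects who receive every scheduled dose, SAP 9 treats missing psychiatric data as random and non-informative, subject to case-by-case review, and imputes nothing further. No rule covers a baseline of 0. For BPRS, by contrast, the SAP does say when a score is not calculable: "If an item is not assessed, the BPRS Total Score will not be computed".

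**Baseline.** The general rule in SAP 5.3 is "Unless otherwise specified, the baseline value will be defined as the last non-missing evaluation prior to the first dose of study drug". SAP 9.2.1 instead says "Baseline will be considered to be on Day -1", and SAP 9.1.1 and 9.4.1 say the same for BPRS and 3MS.

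**3MS.** SAP 9.4.3 writes the 3MS change as the postdose CADSS total minus the 3MS baseline. SAP 9.4.1 gives a total of 0 to 100 and, in its table, a per-item range of 0 to 7.

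**The concern.** Percent change divides by baseline, and healthy volunteers are expected to score close to 0 on CADSS. A subject with a baseline of 0 has no percent-change value at any visit. That removes all six scheduled postdose assessments (6 and 24 hours after dosing on Days 1, 7 and 14). Whether the value is missing is settled entirely by the baseline score, which does not sit with an assumption of random, non-informative missingness. The scale matters here: Protocol Appendix 14 associates mGlu5 inhibitors, including TMP-301, with dissociation, and CADSS is part of the primary safety endpoint.

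The other three items are specification errors. Programmed literally, the Day -1 statements would point the change scores and the model covariate at a day with no assessment of these scales in its column, and the 3MS change would compare two different instruments. The 3MS total cannot reach its stated maximum.

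**Working it through.** **1. CADSS percent change**

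Range: 23 × 0 = 0 to 23 × 4 = 92, which reproduces the SAP. BPRS has a minimum of 18 × 1 = 18, so its percent change is always defined.

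A 2-point rise is 100 × 2/5 = +40% from a baseline of 5, 100 × 2/1 = +200% from 1, and undefined from 0.

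Share of zero baselines, P0. Inputs from SAP 9.2.1: mean m = 1.67, and s = 2.96 assumed to be an SD, so s² = 8.76 and m² = 2.789.

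- Upper bound (Cauchy–Schwarz): P0 ≤ 1 − m²/(s² + m²) = 1 − 2.789/11.551 = 0.759. No positive lower bound follows from these two figures.
- Poisson, matching the mean only: exp(−1.67) = 0.188. Its SD is √1.67 = 1.29, so it does not match 2.96.
- Negative binomial, matching both: r = m²/(s² − m) = 0.393; P0 = (r/(r + m))^r = 0.521.
- Zero-inflated Poisson, matching both: pλ = s²/m − 1 = 4.246; λ = 1.67 + 4.246 = 5.916; p = 0.718; P0 = p + (1 − p)exp(−λ) = 0.718.

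The expected number of evaluable subjects among 6 active, 6 × (1 − P0), is then 4.9, 2.9 or 1.7. These figures are illustrations, not estimates for this trial.

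A threshold that needs no model for the score: with independent subjects and a common probability p, the chance of losing at least one of 6 is 1 − (1 − p)⁶. It equals 0.5 at p = 1 − 0.5^(1/6) = 0.109.

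**2. Baseline day**

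- Protocol Table 3 and SAP Appendix A both put check-in on Day -2. In both, the Day -1 column is the baseline caffeine test and has no BPRS, CADSS or 3MS.
- Protocol 6.1.8 and 6.1.9, and SAP 9.2.1 itself, place the predose assessment at check-in on Day -2.
- SAP 9.4.1 puts the 3MS check-in on Day -1, against the SAP's own schedule.
- SAP 5.3 yields to any specific statement, so the Day -1 statements displace it.

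**3. 3MS change**

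Example: a 3MS baseline of 98 and a postdose CADSS of 2 give 2 − 98 = −96, whatever happened to the 3MS score.

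**4. 3MS scoring**

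- Stated maxima for items 1 to 15: 5+3+5+9+15+5+5+10+6+5+3+5+10+3+9 = 98. The stated 100 is not reproduced.
- Item 3's parts add to 1 + 2 + 1 = 4, not the stated 5. By parts the total is 97.
- The sample form in Protocol Appendix 11 scores Mental Reversal 2 + 5 = 7, and 98 − 5 + 7 = 100 exactly. Keeping the SAP's separate forward-counting point as well gives 1 + 2 + 5 = 8, and 98 − 5 + 8 = 101.
- Items 4, 5, 8, 13 and 15 run to 9, 15, 10, 10 and 9, above the table's 0 to 7.
- The parts of item 10 (Repetition) carry place labels from item 6 (Spatial Orientation). Their maxima, 2 + 1 + 1 + 1 = 5, do match the stated subtotal.

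**The case against.** The strongest objection is that little depends on this endpoint. Raw CADSS values and absolute change, with its contrasts, remain. No stopping or escalation rule uses the derived scores. Protocol Appendix 14 has CADSS responses reviewed for psychiatric adverse events. There is no formal sample-size calculation, only "It is estimated that approximately 24 subjects should be sufficient to meet the objectives of the study" (the planned maximum is 32), so losing a subject breaches no stated power. All of this stands, and it limits the impact.

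The evidence on zeros is also thin: one unlabelled figure, for healthy males, whereas this trial also admits postmenopausal women and excludes psychiatric history. That stands too. A reader might infer that most subjects will be lost, or that the contrasts will be biased towards hiding dissociation. The documents support neither. The reference figure forces no minimum share of zeros, and subjects who stay at 0 drop out along with new-onset cases, so the direction of any distortion is unknown.

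A 3MS total of 0 is also formally possible, but it is not expected in healthy subjects, so 3MS percent change does not share the practical problem. The case-by-case review in SAP 9 makes silent loss less likely, but it is not a rule for a value that cannot be calculated.

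On the baseline day, it would go too far to say that nothing could fall on Day -1. The Screening column in both schedules runs to Day -1, and a footnote allows these scales at other times. However, the protocol synopsis ends Screening at Day -3, so a mislabelled Day -2 check-in is the likelier explanation.

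The 3MS formula is an evident copying slip. The same 3MS table also says that item scoring varies, which softens the 0 to 7 entry but does not make it correct. Protocol Appendix 11 is a sample form, so differences from it are a reason to reconcile and do not prove the SAP wrong.

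**Conclusion.** The plan is wrong as written, with limited impact, and should be corrected before database lock. The substantive point is CADSS percent change. It is a modelled endpoint that is undefined at a permitted and plausible baseline, has no rule for that case, and loses subjects by a mechanism at odds with the SAP's missing-data assumption.

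This rests on the score range and on SAP 9.2.3, 9.2.4 and 9.6, not on any modelled share. The 19% to 72% range assumes that 2.96 is an SD and that the male reference applies. The 11% threshold assumes only independent subjects with a common probability.

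The remaining items are corrections: the Day -1 statements displace a workable general rule, the 3MS change names the wrong scale, and the 3MS maxima fall 2 points (3 by parts) short of the stated total.

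**What to change.** 1. Remove CADSS percent change from the SAP 9.6 model and rely on the absolute change already planned. If it is kept descriptively, state that it is not calculable at a baseline of 0 and show n per group. BPRS and 3MS percent change can stay.
2. Delete the Day -1 baseline statements in SAP 9.1.1, 9.2.1 and 9.4.1 so that SAP 5.3 applies, and correct the 3MS check-in day in 9.4.1.
3. Define 3MS change as postdose 3MS total minus baseline 3MS total.
4. Reconcile 3MS parts, subtotals, per-item range, total and item 10 labels with the version actually administered. Changing item 3's subtotal alone is not enough, because its parts must also add up.

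The cost is SAP wording and programming specifications before database lock. Only the CADSS percent-change contrasts are lost.

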9.2.4 CADSS Analysis

Tables and listings will be presented for absolute values and derived endpoints described below. Inferential analysis will be provided for the derived endpoints (refer to SAP Section 9.6 for more detailed information).

9.3 Columbia-Suicide Severity Rating Scale (C-SSRS)

9.3.1 C-SSRS Assessment

The C-SSRS is a questionnaire designed for the assessment of suicidal ideation and behavior in adolescents and adults.

To monitor for a history of (the past 2 years to present) or for the emergence of suicidal ideation and behavior, subjects will undergo C-SSRS evaluations at Screening, Check-in on Day -2, and within 3 hours prior to dosing on Days 1, 3, 5, 7, 9, 11, 13, 15, 17 and on day 18 prior to Discharge, and at the follow-up/EOS visit.

The C-SSRS will be used to assess both behavior and ideation that tracks all suicidal events and provides a summary of suicidal ideation and behavior. It assesses the lethality of attempts and other features of ideation (frequency, duration, controllability, reasons for ideation, and deterrents), all of which are significantly predictive of completed suicide.

Two versions of the C-SSRS will be used in this study: the Baseline/Screening version (lifetime history and past 12 months) and the Since Last Visit version. The Screening version of the C-SSRS will be administered at the Screening visit. The Since Last Visit version of the C-SSRS will be administered at all subsequent assessment times.

9.3.2 C-SSRS Analysis

A frequency table will be used to summarize Baseline/Screening and Since Last Visit responses for each cohort, and C-SSRS Question, e.g. Wish to be Dead, Non-Specific Thought, Active Ideation (Not Plan) without Intent, Active Ideation with Some Intent, without Plan, Active Ideation with Plan and Intent.

A listing by Baseline/Screening and Since Last Visit responses will be output by cohort, subject, C-SSRS Category, and C-SSRS Question, e.g. Suicidal Ideation: Wish to be Dead, Non-Specific Thought, and Suicidal Behavior: Actual Attempt, Engaged in Non-Suicidal Self-Injurious Behavior?, Interrupted Attempt, Aborted Attempt, Preparatory Acts or Behavior, Suicidal Behavior, Suicide.

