6.1.10. Columbia Suicide Severity Rating Scale (C-SSRS)

The C-SSRS is a questionnaire designed for the assessment of suicidal ideation and behavior in adolescents and adults.

To monitor for a history of (the past 2 years to present) or for the emergence of suicidal ideation and behavior, subjects will undergo C-SSRS evaluations at the time points indicated in [Table 3](#).

The questionnaire must be administered by a psychiatrist or other individual that is suitably qualified by education or training. See [Appendix 9](#) for a sample C-SSRS – Baseline/Screening version assessment and [Appendix 10](#) for a sample postdose C-SSRS (Since Last Visit Version) assessment.

The C-SSRS will be completed at screening, check-in on Day -2 and it will be assessed approximately 3 hours prior to dosing on Days 1, 3, 5, 7, 9, 11, 13, 15, 17 and on day 18 prior to discharge, and at the follow-up/EOS visit.

PD procedures should be carried out in the following order when required: (1) 3MS, (2) CADSS, (3) BPRS, (4) C-SSRS.

If there is a positive result for suicidality on the C-SSRS after Screening (defined by a subject answering “yes” to questions 4 or 5 on the suicidal ideation portion of the C-SSRS), the subject will be evaluated by an Investigator or medically qualified sub-investigator for continuation in the study.

If a subject becomes suicidal during the study, an Investigator or medically qualified sub-investigator should provide the appropriate treatment to the subject.

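### The C-SSRS table is split by form version, with no visit or first-dose split stated, so two pre-treatment forms per subject share a stratum with on-treatment responses

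*SAP*

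**What the plan says.** SAP 9.3.2 defines the C-SSRS frequency table by form version, cohort and question: "A frequency table will be used to summarize Baseline/Screening and Since Last Visit responses for each cohort, and C-SSRS Question". The listing has a similar structure: "A listing by Baseline/Screening and Since Last Visit responses will be output by cohort, subject, C-SSRS Category, and C-SSRS Question". Neither sentence names visit, time point or a split at the first dose.

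SAP 9.3.1 says what the two form versions are and when each is used. They are "the Baseline/Screening version (lifetime history and past 12 months) and the Since Last Visit version". On timing: "The Screening version of the C-SSRS will be administered at the Screening visit". Then: "The Since Last Visit version of the C-SSRS will be administered at all subsequent assessment times". The assessment times in the same section are Screening, "Check-in on Day -2, and within 3 hours prior to dosing on Days 1, 3, 5, 7, 9, 11, 13, 15, 17", Day 18 before discharge, and the follow-up/EOS visit. Protocol 6.1.10 gives the same time points: "The C-SSRS will be completed at screening, check-in on Day -2 and it will be assessed approximately 3 hours prior to dosing on Days 1" and the alternate days that follow. However, where it points to its Appendix 10, the protocol describes the Since Last Visit version as the form for use after dosing.

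Two other SAP sections bear on the point. Section 9.6 has a general sentence on summarising psychiatric measures at each time point by treatment. Section 13 places table layouts in a separate document.

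**The concern.** Baseline/Screening and Since Last Visit are names of questionnaire versions, not of treatment phases. If SAP 9.3.1 is followed, the second version is completed twice before any study drug is given. A table split by version then puts a yes given at Check-in or before the first dose into the same cell as a yes given on treatment. A reader will tend to take that cell as post-treatment, the more so because the protocol describes the form that way.

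The C-SSRS is a component of the primary safety endpoint (Protocol section 2). Protocol 6.1.10 says it is there to pick up history and emergence of suicidal ideation and behaviour, and Protocol Appendix 14 associates this drug class, including TMP-301, with psychiatric adverse events. With six active subjects per cohort, one case placed in the wrong phase is visible in the table, and the SAP defines no treatment-emergent C-SSRS outcome that would correct the impression.

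**Working it through.** The plan gives no figure to reproduce here, so the check is a count and some day arithmetic.

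1. **Scheduled Since Last Visit forms per subject** (SAP 9.3.1, Protocol 6.1.10): Day -2; Day 1 predose; Days 3, 5, 7, 9, 11, 13, 15, 17; Day 18; EOS. That is 1 + 1 + 8 + 1 + 1 = 12. Before the first dose: Day -2 and Day 1, so 2/12 = 17%. After the first dose: 10.

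2. **Look-back time covered by those forms.** There is no Day 0, and EOS is taken at its nominal Day 25.
   - After first dose: Day 1 to Day 25 = 24 days.
   - Before first dose, Screening on Day -28: 26 days to Day -2, plus 2 days to Day 1 = 28 days. Share = 28/(28 + 24) = 54%.
   - Before first dose, Screening on Day -3 (the latest day in the protocol synopsis): 1 + 2 = 3 days. Share = 3/(3 + 24) = 11%.

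   The untreated share of look-back time is therefore 11% to 54%.

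3. **Effect of one subject.** Each cohort has 6 active and 2 placebo subjects (SAP 3.1). One subject positive only before dosing adds 1/6 = 17 percentage points to an active group, or 1/8 = 12.5 points if the table is read by whole cohort.

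4. **Can such a subject be dosed?** The exclusion criteria (Protocol 4.2) contain no C-SSRS criterion. Protocol 6.1.10 calls for evaluation for continuation after a yes to ideation question 4 or 5, and states no action for questions 1 to 3. So a subject with a pre-dose positive answer can enter the Safety population. Limiting the table to that population removes undosed subjects, not the pre-dose records of dosed ones.

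5. **How often?** The documents give no rate. As an assumption only, take a pre-treatment positive rate q of 1% to 5% per subject. The chance of at least one such case among n subjects is 1 - (1 - q)^n: 6% to 26% for n = 6, and 8% to 34% for n = 8.

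6. **After a split at first dose.** The on/post-treatment row would use only the 10 forms from Day 3 to EOS. The Day 1 form is completed within about 3 hours before the first dose, so existing data separate almost exactly at that point.

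**The case against.** **SAP 9.6 already promises a summary at each time point.** The C-SSRS is one of the listed psychiatric assessments. The lack of a cross-reference from 9.3.2 is not decisive, because the VAS analysis section does not refer to 9.6 either and 9.6 clearly covers the VAS. This has weight. But the statistics in 9.6 (mean, SE, quartiles) suit numeric scores and not yes/no answers, and 9.3.2 specifies its own table.

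**The shells may show visit.** Nothing in 9.3.2 says that responses are collapsed over visits, so a by-visit layout is compatible with the text. It is not a commitment, though. The SAP names visit for laboratory tests (8.2), vital signs (8.3), ECG (8.4) and the physical examination listing (8.5), but not here.

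**The protocol may mean the Since Last Visit form for post-dose use only.** If the site used another form at Day -2 and Day 1, form version would separate the phases and no mixing would occur. SAP 9.3.1 is explicit the other way. The protocol label appears where it points to a sample form and does not assign a form to each visit. What stands is a conflict between the two documents that has to be resolved.

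**Positive answers should be uncommon, and the data are not lost.** Subjects are healthy, those with a DSM-5 disorder are excluded, and responses are listed by subject. All true. The listing text does not name visit, however, so it does not by itself show when an answer was given.

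**Conclusion.** The concern holds in a limited form. As SAP 9.3.1 and 9.3.2 are written, 2 of 12 scheduled Since Last Visit forms per subject are pre-treatment and share a stratum with on-treatment responses. Those forms carry 11% to 54% of the look-back time, and one affected subject moves an active group by 17 points. This assumes that the site follows SAP 9.3.1 on form version and that the table has only the dimensions that 9.3.2 names.

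Three stronger readings are tempting, and the documents do not support them:

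- A reader might infer that the analysis cannot show emergence of ideation, or that this table is certainly the only C-SSRS summary. SAP 9.6 and the unseen shells leave room for a by-visit display. What is missing is a requirement for one.
- A reader might infer a breach of the baseline rule in SAP 5.3. That section sets a default baseline value, and the C-SSRS has no change-from-baseline endpoint, unlike BPRS, CADSS and 3MS. Not using the rule here does not contradict it.
- A reader might take 54% as a misallocation rate. It is the upper limit of a share of recall time, reached only with Screening on Day -28. It says nothing about how many subjects will be misplaced.

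The change is still worth making: the C-SSRS is part of the primary safety endpoint, groups are small, and the data needed are already collected.

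**What to change.** In SAP 9.3.2:

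- Tabulate by treatment phase, or by visit. Pre-treatment is Screening, Check-in and Day 1 predose; on/post-treatment is Day 3 to EOS.
- Show lifetime history from the Screening form separately.
- Define treatment-emergent ideation or behaviour as a worst post-dose category higher than the worst recent pre-treatment category. Recent means the Check-in and Day 1 predose forms, plus the Screening recent-period responses if wanted. Leave lifetime responses out of the comparison: otherwise remote ideation would mask new on-drug ideation of the same or a lower category.
- If Screening recent-period responses are used, name the period, since SAP 9.3.1 mentions both two years and 12 months.
- Add visit to the listing.

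Reconcile Protocol 6.1.10 with SAP 9.3.1 on which form is used at Day -2 and Day 1, and align the protocol's description of the Since Last Visit form with the answer.

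For the analysis, the cost is SAP wording and one table shell, with no new data. The reconciliation is a clarification of text.
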